4.5 Vulnerable Populations

Children, pregnant women, fetuses, neonates, or prisoners are not included in this research study. Educationally or economically disadvantaged persons are included but not solely targeted for recruitment. Because of our recruitment efforts for this study, it is possible that University of Pennsylvania employees and students may be invited to participate. Status of participation in the current study will be independent of the participant's work or school activities. Special protections and/or additional safeguards will be undertaken in order to protect the rights and welfare of these subject groups from coercion or undue influence as appropriate.

4.6 Subject Recruitment

Participants may be recruited from television, radio, internet advertisements, newspaper, flyers, transit posters, referrals, and/or from our database of previous participants who have agreed to be re-contacted for future studies. Interested participants will complete a telephone screen to assess initial eligibility. Those who are initially eligible will be screened against our registration database to confirm that they are not currently participating in another research study at our Center and have not previously reported a condition or circumstance that would make them ineligible for the current study. They will then attend an Intake Visit at our Center during which the purpose and procedures of this study will be described to them and final eligibility will be confirmed. Participants may complete intake session measures remotely to verify initial eligibility before an in-person visit is scheduled. All advertising materials will be submitted to the UPENN IRB for approval prior to distribution/posting.

Referral Bonus Program

CONFIDENTIAL

This material is the property of the University of Pennsylvania. Do not disclose or use except as authorized in writing by the study sponsor

Participants who achieve their final scans (day 4 or day 32) will be given the opportunity to receive a small bonus for referring others to the program. If the person who is referred completes the initial eligibility phone screen, regardless of outcome, the study participant will be awarded \$20 per referral, for a maximum of 3 referrals (\$60). This has been successfully implemented in IRB protocols #828125 and #824504.

4.7 Early Withdrawal of Subjects

4.7.1 When and How to Withdraw Subjects

Subjects are free to withdraw from the study at any time. Subjects may be deemed “ineligible” at any time per the exclusion criteria listed in section 4.5. No follow-up data collection is required for participants who withdraw or are deemed ineligible throughout the study.

5 Study Procedures

5.1 Telephone Eligibility Screen

Individuals interested in study participation will be screened by a qualified member of the research team to determine initial study eligibility. If the participant meets preliminary eligibility, they will be invited to schedule an Intake Visit at which their final eligibility will be confirmed.

5.2 In-Center Visits

In an effort to increase the safety of participant visits, while also increasing the efficiency of study procedures in light of COVID-19, study staff will be implementing electronic data collection for various study measures. Specific measures that can be collected remotely are listed below for each visit with three asterisks (***)�.

5.2.1 Visit Reminders

Participants will typically receive study visit reminders 24 – 48 hours prior to their scheduled study visits via by text message (if applicable) via the W2H software platform. Participants who cannot receive text reminders or who do not agree to receive text reminders will still be able to participate and will receive reminders via phone call or email.

Way to Health (W2H) is a software platform developed by the Penn Center for Health Incentives and Behavioral Economics (CHIBE), operated through a partnership between CHIBE and the Penn Medicine Center for Health Care Innovation and housed on Penn Medicine Academic Computing Services (PMACS) servers. W2H is an integrated, cloud-based platform that blends behavioral science with scalable digital technology to improve clinical outcomes. W2H automates many research functions necessary for conducting randomized controlled trials of healthy behavior interventions.

5.2.2 Intake Visit (~ day -14)

During the Intake Visit (Duration: ~3 hours) participants will:

1. Hear an informed consent and HIPAA presentation where all the study procedures and institutional policies will be reviewed.***
 - The combined informed consent and HIPAA form will be read verbatim. All participant questions will be answered as appropriate after which the combined informed consent and HIPAA form will be completed (signed and dated) by both the participant and a qualified member of the research team.

CONFIDENTIAL

This material is the property of the University of Pennsylvania. Do not disclose or use except as authorized in writing by the study sponsor

2. Confirm the accuracy of information (i.e. name, address, phone number, email [if applicable], date of birth, age, gender, ethnicity, and race) provided during the initial Telephone Eligibility Screen***.

Complete a UDS (at least 30ml [two tablespoons] of urine). The UDS will assess the use of any study-prohibited medications/recreational drugs (See Key Exclusionary Criteria; Alcohol and Drug).

- Participants who test positive for any exclusionary medications or recreational drugs per this protocol will be deemed ineligible.

3. Female participants only: Self-administer a CLIA-waived urine pregnancy test.
 - Female participants are informed that the participation of pregnant women in this study is prohibited and that if they believe they are pregnant they should withdraw from the study immediately.
4. Perform a BrAC assessment to control for alcohol consumption.
 - Participants with a BrAC greater than 0.000 at Intake Visit will be ineligible.
5. Perform a CO breath assessment and self-report smoking behavior over the past 24 hours to control for prior tobacco exposure.
 - Participants in the smoking group with a CO reading less than 8 ppm will be deemed ineligible.
 - Participants in the non-smoking control group with a CO reading greater than 5ppm will be deemed ineligible.
6. Complete height and weight measurements. Participants weighing over 275lbs will be excluded.
7. Complete a Medical History Form with a member of the research team to review for applicable contraindications previously listed under Inclusion and Exclusion Criteria (section 4.4 and 4.5).***
8. Complete an fMRI Medical History Form, Magnet Safety Form, and Emergency Contact Form.***
9. Complete the Shipley Institute of Living Scale IQ test.
 - Participants earning less than an estimated WAIS-R IQ score of 80 will be deemed ineligible.
10. Complete paper and pencil questionnaires:
 - Demographics***
 - Smoking History/Nicotine Dependence (FTND)***
 - ETOH History***
 - Cigarette Brand Form (staff will record cigarette brand information)***
11. Schedule study track with a trained staff member & complete compensation paperwork.

5.2.3 Baseline Visit (Day -7)

Participants are asked to not consume food or caffeine for 4 hours prior to the beginning of the visit. During the Baseline Visit (Duration: ~3 hours) participants will:

1. Complete a UDS (at least 30ml [two tablespoons] of urine). The UDS will assess the use of any study-prohibited medications/recreational drugs (See Key Exclusionary Criteria; Alcohol and Drug).
 - Participants who test positive for any exclusionary medications or recreational drugs per this protocol will be deemed ineligible.

CONFIDENTIAL

This material is the property of the University of Pennsylvania. Do not disclose or use except as authorized in writing by the study sponsor

2. Perform a BrAC assessment to control for alcohol consumption.
 - Participants with a BrAC greater than 0.000 at Baseline Visit will be ineligible to proceed with the visit. The Principal Investigator may permit the participant to reschedule the visit to another day.
3. Perform a CO breath assessment & daily smoking rate (timeline follow back [TLFB]) (smokers only).
4. Self-report smoking behavior over the past 24 hours to control for prior tobacco exposure and provide their daily smoking rate (timeline follow back [TLFB]) (smokers only).
5. Have weight measured.
6. Complete paper and pencil questionnaires:
 - Withdrawal Symptoms (MNWS)***
 - Smoking Urges/Craving (QSU-B)***
 - Depression Symptoms (CES-D)***
 - Positive & Negative Affect (PANAS)***
 - Eating Behavior (DEBQ)***
 - Eating Inventory-Disinhibition (EI-D)***
 - Weight Concerns***
7. Immediately prior to the laboratory tasks, participants will be asked to rate, "How hungry are you right now?" using a scale from 0 "not at all" to 10 "extremely."***
8. Participants will be provided with a Boost® Nutritional Drink to consume prior to completing the laboratory tasks.
9. Complete the Individualized Food (Pre-FCQ-S) task. Foods rated least appetizing (n=20) and foods rated most appetizing (n=20) will be selected to create personalized food cue stimuli for the Food Cue-Induced Craving (FCQ-S) task administered over the course of the study.
10. Select either the salty (Lay's® Classic Potato Chips) or sweet (M&M's® [Milk Chocolate]) snack food as the snack to "work for" (Pre-RRVF) in the Relative Reinforcing Value of Food (RRVF) task over the course of the study.
11. Complete computerized laboratory tasks:
 - Food reward
 - Working memory (N-back)
12. Immediately after the laboratory tasks, participants will be asked to rate, "How hungry are you right now?" using a scale from 0 "not at all" to 10 "extremely."***

5.2.4 Mandatory Abstinence Period for Smoking Group (~days 1-3 or 29-31)

Participants will be randomized with respect to the order of the study periods; one-half of participants will have their mandatory abstinence period on days 1-4 and one-half will have this period on days 29-32. On the evening prior to the mandatory abstinence period, participants will receive a 20-minute structured telephone counseling session from a trained smoking cessation counselor to prepare for the upcoming 4-day abstinence period. Quit strategies include identifying triggers and alternative behaviors to smoking, deep breathing, and stimulus control methods. The abstinence periods will be framed as "practice quit attempts" unaided by nicotine replacement therapy or other medication.

On study days 1-3 (period 1) and 29-31 (period 2), participants will come to the Center and complete measures that may include a CO reading, breath alcohol test (BrAC), and questionnaires (smoking behavior, urges, mood, withdrawal, eating). Please see measures

CONFIDENTIAL

This material is the property of the University of Pennsylvania. Do not disclose or use except as authorized in writing by the study sponsor

table for specific time points. To verify smoking abstinence participants must have a CO reading of <10ppm or >50% reduction from their intake CO value on day 1 (or 29) and a CO reading of <5ppm on days 2, 3, or 4 (or 30, 31 & 32). Participants that do not meet CO criteria, have a BrAC greater than 0.000, or a positive urine drug screen will be withdrawn from the study, unless the Principal Investigator permits the participant to reschedule the visit to a later date.

Day 1/Day 29 Back-up Scheduling: Some participants may choose to be scheduled as a back-up for another participant's Day 1 or Day 29 visit. This is done to ensure that this protocol is efficiently using the time that is reserved on the fMRI scanner days at Days 4 and 32. Participants who are scheduled as a back-up should prepare for their back-up Day1/Day 29 in the same way that they would prepare for a primary visit. On the day of the back-up, participants should arrive at the Center in the smoking state that they have been assigned to for their respective Day 1/Day 29. Upon arrival participants will go through the same visit check-in to verify eligibility for the visit.

If the primary participant for that day attends their visit and is eligible to proceed then the back-up participant will be compensated \$25 for their time and will be able to leave the center and will attend their Day 1/Day 29 visit as scheduled. If the primary participant for that day becomes ineligible for any reason or does not attend their visit the back-up participant will be promoted to primary and will continue on with the appointment as their Day 1/Day 29 session. Participants who are promoted to primary will then be compensated as per the usual Day 1/Day29 compensation plan.

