2.2 Overall Objectives - (Recruitment & Retention Pilot Study)

Aim 1: To evaluate the effects of information provision and incentives, alone and in combination, on study enrollment rates.

Hypothesis: Behavioral economic interventions will (Information provision & contingency management) will produce higher rates of enrollment compared to standard recruitment.

3 Study Design

General Design – Main Study

This is a within-subject cross-over neuroimaging investigation of 3 potential neural mechanisms of increased caloric intake during initial smoking cessation. Eighty smokers will be scanned on 2 occasions: (1) after 4 days of monitored abstinence (biochemically verified), and (2) after 4 days of smoking as usual (order counterbalanced) (**Figure 3**). In addition, 30 healthy non-smokers (matched for sex, age, and education) will complete one period of the study to serve as a baseline comparison group (see Exploratory Aim). As in prior studies, participants will have fasted overnight and be provided with a standard meal (BOOST® shake) when they arrive on testing days 4 and 32. Blood oxygen level dependent (BOLD) fMRI sessions will assess BOLD signal at rest and while performing tasks for food cue reactivity, food reinforcement (choice task), and working memory (N-back). Additional measures will be administered out of scanner (**Figure 3**). Caloric intake will be assessed on days 1-3 and 29-31 using a validated dietary recall procedure (days 4 and 32 are fMRI scan days and intake will be standardized). Caloric intake is the primary behavioral outcome. Task-induced BOLD signal change in hypothesized regions of interest and performance on the working memory, food cue, and food reinforcement tasks are the mechanistic variables.

CONFIDENTIAL

This material is the property of the University of Pennsylvania. Do not disclose or use except as authorized in writing by the study sponsor

Figure 3

Non-smoker Control Group (Baseline):

Day	-7	1 2 3 4
Activity	Intake	Period 1*

*non-smokers complete phase 1 with identical monitoring and assessment

**order of periods (abstinence vs smoking) is counter balanced

Smoker Group (within-subject):

Day	-7	1 2 3 4	5-28	29 30 31 32	1 Month Follow-up
Activity	Intake	Period 1	Washout	Period 2	Web-based Survey
State	Smoke	Abstain**	Smoke	Smoke	N/A

Behavioral Outcome:

- Caloric intake (dietary recall; Days 1-3* & Days 29-32)

Intermediate Outcomes: Day 4* & Day 32

- Food reward (out of scanner)
- Working memory (fMRI)

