- Food cue reactivity (fMRI)
- Food reinforcement (fMRI)

Smoking Behavior: Days 1-4* and 29-32

- Self-reported (CO-verified)

Recruitment & Retention Pilot

This pilot study will utilize a randomized controlled trial design to evaluate two components of behavioral economic strategies to improve recruitment and retention. To be eligible for the pilot study participants must meet all eligibility criteria for one of the four participating studies (828958, 824061, 824860, 828125), have a phone capable of receiving SMS messages, and consent to receive SMS messages. ~576 participants will be enrolled across the four participating research studies. All subjects will receive standard text messages and will be randomized to one of four groups (blocked within each study to ensure balanced groups): (1) Standard recruitment (SR): subjects will receive text messages ~2 days prior to their Intake visit with relevant information about the time, date, and location of the visit as well as contact information for study staff ("You have a study visit on [Date] at [Time]. Visit comp is \$10. Reply Y to confirm. See <http://j.mp/2222222> for reminders. Reply or appt may be canceled."); (2) SR + Information Provision (IP): Subjects will receive personalized messages designed to target injunctive norms regarding participating in research (e.g., "[Name], wondering why you should volunteer for research? Many find it a rewarding way to advance science and be a part of a community <http://j.mp/2222222>."); (3) SR + Contingency Management (CM): CM will be provided in the form of an opaque "fishbowl" with a high proportion of chips with little (\$1) monetary value. Participants draw from the fishbowl upon completion of an objectively verified target behavior (e.g., attending an Intake visit), and bonuses are often provided for continued performance [74, 75]. This strategy has been successful in augmenting visit compliance in several treatment studies [80-82]. All text reminders will be delivered using the Way 2 Health (W2H) software platform. Upon completion of all requirements for a given visit, participants will receive 5 fishbowl draws for that visit. Attendance at all visits earns participants bonus draws upon completion of the study. Failure to attend a visit without prior approval or failure to complete all visit requirements results in no draws for that visit. The fishbowl contains 500 chips: 250 say "good job," 219 have a value of \$1, 30 have a value of \$5, and 1 has a value of \$100. The study completion bonus will be 5 extra draws. Thus, at each visit, subjects will have the opportunity to make 5 draws from the fishbowl, for maximum possible earnings of \$120; (4) SR + IP + CM (IC): In this group, subjects will receive the targeted text messages and receive CM.

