Eating Behavior (DEBQ)***: The Dutch Eating Behavior Questionnaire will assess restrained eating (10 items, tendency to restrict food intake), external eating (10 items, tendency to eat in response to food related cues) and emotional eating (13 items, tendency to eat in response to emotions). These scales are associated with food craving and response to food cues. Participants indicate on a Likert-style scale how often each item is applicable to them (0= not relevant; 1 = never to 5=very often).

Eating Inventory-Disinhibition (EI-D)***: Disinhibition will be measured with a subscale (16 items) of the Eating Inventory that is thought to reflect responsivity to environmental food cues, and internal cues, and linked to food reinforcement and weight change.

Carbon Monoxide (CO): CO will be measured at the Intake Visit for all participants and at all subsequent in-person visits to confirm smoking status of the smoking group. The CO monitor is a handheld device that uses a disposable mouthpiece, reports CO in parts per million (ppm), and takes about 3-5 minutes to administer.

Depression Symptoms (CES-D)***: The Center for Epidemiologic Studies Depression Scale is a 20-item Likert-style scale used to assess depressive symptomatology. This scale has high internal consistency ($r=.85-.90$) and has been shown to correlate with clinical ratings of the severity of depression. In our previous research, CES-D scores have correlated significantly with self-medication smoking and nicotine dependence.

Smoking Urges/Craving (QSU-B)***: The well-validated and reliable 10-item brief Questionnaire of Smoking Urges will assess craving for cigarettes. The QSU-B utilizes a "right now" frame of reference.

Weight Concerns***: Weight concerns associated with quitting smoking will be measured with a reliable ($\alpha=.87$) and valid 6-item scale. Responses to the 6 items range from 1 (not at all) to 10 (very much). Scores are the average of responses to all items.

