Missing Values. As with most studies, we expect to have some degree of missing data. We will assess the extent and type of missing data and select the most appropriate method for dealing with missing data (e.g., multiple imputation). For example, for items missing at random on survey measures, missing items can be imputed prior to calculating final scores using conditional means, estimated with an iterated version of Buck's method. A less common but

CONFIDENTIAL

This material is the property of the University of Pennsylvania. Do not disclose or use except as authorized in writing by the study sponsor

more important cause of missing data is differential dropout, which can cause imbalances in the randomization. We will examine the characteristics of those subjects who drop out, paying particular attention to whether there is an association between dropout and abstinence sequence. These analyses will be descriptive, as we expect few dropouts.

6 Risks / Benefits

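### The CO rule for verified abstinence joins its days with *or* in period 1 and *&* in period 2; probably a slip, but read literally it sets a different standard for each randomised order

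*Combined protocol and SAP*

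**What the plan says.** Section 5.2.4 randomises the order of the two periods: "one-half of participants will have their mandatory abstinence period on days 1-4 and one-half will have this period on days 29-32". Abstinence is verified in two steps.

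- **First day:** "a CO reading of <10ppm or >50% reduction from their intake CO value on day 1 (or 29"). This is the same in both periods.
- **Remaining days:** "a CO reading of <5ppm on days 2, 3, or 4 (or 30, 31 & 32"). The period 1 days are joined by *or*, the period 2 days by *&*.

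Participants who miss the CO criteria "will be withdrawn from the study, unless the Principal Investigator permits the participant to reschedule the visit to a later date".

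Elsewhere the two periods are treated alike. Section 3 (General Design – Main Study) has smokers scanned "after 4 days of monitored abstinence (biochemically verified"), whichever order they are in. Figure 3 lists "Smoking Behavior: Days 1-4* and 29-32" as self-reported and CO-verified. Table 2 schedules CO for smokers on each of days 1-4 and 29-32. Section 5.3.1 has CO measured "at all subsequent in-person visits to confirm smoking status of the smoking group". None of these gives a day-specific cut-off.

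**The concern.** Abstinence is the exposure in this crossover, and the sentence in Section 5.2.4 is its only operational definition. The sentence decides who is withdrawn and who is analysed as abstinent. If its two halves were followed as written, both decisions would depend on randomised order.

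Three things would be at stake.

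- **Meaning of the difference score.** Section 5.6 analyses Aims 1 and 2 through abstinent-minus-smoking differences. Under an order-dependent rule, the abstinent half of that difference would be verified to one standard in one sequence and to another standard in the other.
- **Retention.** CO-based withdrawal could be more frequent among those who abstain second.
- **Protection in the analysis.** The covariates that Section 5.6 allows for Aim 1 are sex, BMI, nicotine dependence, age and weight concerns. Sequence and period are not among them.

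**Working it through.** The plan states no figure that depends on this rule, so there is nothing to reproduce. The check is mainly textual.

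**1. The two halves side by side**

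| | Abstain first | Abstain second |
|---|---|---|
| First-day check | day 1: below 10 ppm, or more than 50% below intake | day 29: same |
| Later threshold | below 5 ppm | below 5 ppm |
| Later days | 2, 3 *or* 4 | 30, 31 *&* 32 |
| Literal requirement | at least one of three readings | all three readings |

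Only the connector differs.

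**2. Whether another section settles it.** Section 3, Figure 3, Table 2, Section 5.2.5 and Section 5.3.1 were compared. They imply one standard for both orders, but none states a cut-off by day or says which connector is meant.

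**3. What the literal *or* would admit.** Caloric intake is assessed for days 1-3 and the scan is on day 4.

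- A participant who passes the first-day check and is below 5 ppm on day 2 only would be scanned as abstinent after two readings at or above 5 ppm, one of them on the scan day.
- A participant below 5 ppm on day 4 only would have intake counted as abstinent although the day 2 and day 3 readings were not below 5 ppm.

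Neither case fits four days of biochemically verified abstinence.

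**4. Illustration of the gap.** Let *q* be the probability that a given day's reading is below 5 ppm. No value of *q* is in the documents, so a range is assumed. If the three days are independent:

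- any of three: 1 − (1 − *q*)³
- all three: *q*³

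| *q* | any of three | all three |
|---|---|---|
| 0.3 | 1 − 0.7³ = 0.657 | 0.3³ = 0.027 |
| 0.5 | 1 − 0.5³ = 0.875 | 0.5³ = 0.125 |
| 0.7 | 1 − 0.3³ = 0.973 | 0.7³ = 0.343 |
| 0.9 | 1 − 0.1³ = 0.999 | 0.9³ = 0.729 |
| 0.95 | 1 − 0.05³ = 0.9999 | 0.95³ = 0.857 |

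Readings from one person on consecutive days are likely to be positively correlated, so independence overstates the gap. At the extreme where a person passes or fails on all three days together, both columns equal *q* and the gap is zero. The direction cannot reverse, because passing on all three days implies passing on at least one. The table leaves out the first-day check and the option to reschedule, so it does not give retention rates for this trial.

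**The case against.** The strongest reply is that the literal reading is the least plausible one.

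- The parenthesis is offered as the period 2 counterpart of the same clause, just as day 29 is for day 1 earlier in the sentence.
- The withdraw-or-reschedule sentence works visit by visit. Under any-of-three, a high reading on day 2 or 3 could not by itself fail anyone; failure would be known only on day 4.
- The *or* can be read as meaning whichever of those visits is being checked.
- The CO schedule is the same in both periods.

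All of this stands, and it makes a drafting slip the likely explanation. It does not remove the ambiguity, because no other section supplies the rule. Staff applying the sentence, or an analyst coding abstinence from it, could reasonably reach different answers.

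A second reply is that Section 5.6 already plans to look at dropouts, "paying particular attention to whether there is an association between dropout and abstinence sequence". That is relevant and partly meets the retention concern. But the check is descriptive, is not specific to CO-based withdrawal, and does not address participants retained under different standards.

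A reader might go further and infer that lapsed smokers were in fact kept in one order and withdrawn in the other, diluting the effect and causing differential dropout. The documents do not support that. They show inconsistent wording. They do not show that staff applied two rules or that anyone chose an order-dependent one.

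**Conclusion.** The inconsistency is real and needs correcting, because it lies in the sole definition of the exposure and the criterion for CO-based withdrawal. The conclusion is conditional: **if** the sentence is applied literally, retention and the meaning of abstinent depend on randomised order, and the *or* half conflicts with the design statement in Section 3. That verification actually differed is not shown.

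The size of any bias cannot be derived from the documents. The any-versus-all probabilities compare two readings of a phrase, rest on assumed values of *q*, and overstate the gap to the extent that readings are positively correlated. They should not be read as an estimate of misclassification or dropout in this trial. Which connector was intended is for the sponsor to say.

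**What to change.** 1. **Reconcile the sentence.** The sponsor should reword Section 5.2.4 so that one identical CO rule, with one connector, applies to days 2-4 and to days 30-32, and should record which rule staff have been applying. Cost: one sentence and a short note.
2. **Derive one flag.** Before analysis, derive abstinence status for all retained participants in both orders from the daily CO readings under that single rule. Table 2 already schedules those readings, so this is a recode.
3. **Report withdrawals by sequence.** Extend the descriptive dropout check in Section 5.6 to count CO-based withdrawals, and reschedulings permitted by the Principal Investigator, in each order. Cost: one table.

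Recoding has a limit that should be stated. Section 4.7.1 requires no further data from withdrawn participants. A flag can apply a stricter reading to those retained, but it cannot restore anyone already withdrawn if the looser reading is the one adopted. For those participants the by-sequence report is the only remedy.
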